meta-analyses. With a final expected sample size of 215 (86, 86, 54 in Tele-Savvy (TS), attention control (AC), and usual care (UC) groups respectively), for the primary intervention test (group-by-time effect) comparing the outcomes of the three group changes from T1 to T2 to T3 (3-by-3 repeated measures design of three groups measured at three time points), at 80% power and 5% significance level, small-to-moderate effect sizes, Cohen's $f = 0.21-0.24$ may be detected for the main effects for group, time and group-by-time interaction effects (given moderate correlation between measurement pairs of $r=0.3-0.5$) (power analysis using PASS 14 Power Analysis and Sample Size Software (2015). NCSS, LLC. Kaysville, Utah, USA, ncss.com/software/pass). After adjusting for any potential group differences, the overall intervention effect of the Tele-Savvy program for the combined T1-to-T3 pre-post effects for the immediate Tele-Savvy group plus the T3-to-T5 pre-post effects from the AC and UC groups will yield a total estimated 215 subjects to perform a pre-post test to detect a small effect size of $d=0.19$ at 80% power and 5% significance level. With the pooled sample, we will be able to also test the mediating effects of mastery and self-efficacy on the Tele-Savvy program for the caregiver outcomes. As shown by Fritz and MacKinnon (2007), sample sizes of 148-196 were adequate to achieve 80% power to detect small-to-moderate effect sizes for the indirect effect of the independent variable on the dependent variable through the mediating variable considering both the Sobel test as well as percentile and bias-corrected bootstrapped approaches.¹⁰⁸ Although our analytic strategy is robust to missing data we will enroll 270 CGs (108 for TS and AC groups and 54 for UC group) per consideration 1 above (maximize accommodation) allowing for an expected 20% attrition. For the exploratory aim comparing the program's efficacy across the 3 ethnicity groups, with an expected final sample size of 215 subjects and proportions of approximately 65% Caucasian, 20% African American, 15% Hispanic, at 80% and 5% level of significance, we will be able to detect moderate effect sizes Cohen's $f=0.19-0.23$ (for 3-group by 2-time point RM-ANOVA for group, time and group-by-time effects).

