intervention. We will be able to track, for each participant, which daily videos were viewed, when they were viewed and in what pattern (e.g., daily or in a batch), and how often. Attendance in the videoconferences will be recorded. We will also document any indications – through participant complaints or the Navigator's log – of participant burden (e.g., complaints voiced during interviews or need to split interviews over multiple sessions) and reports of barriers to participation (e.g., CGs unable to join call, quality of audio/video).

Data Management and Analysis Plan Data will be entered at the time of each interview directly into the dedicated project tablet computer and saved on Emory's secure REDCAP platform. All data entry screens are set up in REDCAP and, where possible, include data delimiters (i.e., skip patterns, valid range limits) to ensure correctness and minimize missing data. Data will be exported into SPSS weekly and syntax run for cleaning, further data verification and file concatenation.

Data integrity checks. After each cohort data-gathering point, all data will be merged in SPSS for scale computation, aggregation, and inferential analysis. In preliminary analyses, descriptive statistics and frequency distributions will be examined to identify outliers and ensure integrity of merged files. For all multi-item scales, internal consistency will be examined using Cronbach's alpha and associated statistics (e.g., item-total correlations, alpha if item deleted). Formal test-retest/inter-rater reliability coefficients will be computed as data are concatenated.

Analytic approach. Preliminary analyses will examine baseline differences among completers and non-completers and by study arm (immediate/attention control/usual care) as a randomization check using means/SDs/Inter-quartile range and t-tests for continuous variables and counts/percentages and N-Par/Chi-Square tests for categorical variables. The association of predisposing factors (demographics, CG history, relationship and care recipient status at baseline) with baseline data as well as change in outcomes over time will be examined using goodness of fit, variance analysis, or correlational techniques depending upon measurement characteristics of variables involved. Where significant baseline associations are detected, these potential confounders will be controlled in subsequent tests of major hypotheses through use of covariates/model adjustments.

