Aims 1, 2 and 3 (a). Our primary aims are concerned with assessing the effect of the Tele-Savvy program for reducing or retarding the burden, depression, and anxiety of Alzheimer's family caregiving, promoting the quality of life of persons with Alzheimer's (BPSD, agitation; Quality of Life; affect), and enhancing caregiver mastery. We will employ multi-level mixed effects models (MLM) with random (participant) and fixed (cohort) effects to test linear (and non-linear) trajectories of change for the intervention groups and model group X time and group*time interactions. To compare the Tele-Savvy intervention to the attention control and usual care groups, the first 3 time points will be used to test for differences between the 3 group longitudinal trajectories. Additionally, we will combine the intervention effects for the three groups across the main 3 time points from just before receipt of the intervention to immediately after the intervention to the 1st follow-up time point (T1-to-T2-to-T3 for the immediate group and T3-to-T4-to-T5 for the attention control and usual care groups respectively). These combined time points will be referred to as cT1, cT2, cT3. If there are significant differences between or among the 3 groups at the time point immediately prior to receipt of the intervention (cT1), these "baseline" effects will be included and adjusted for in the final model. Overall time effects will be assessed as well as planned post hoc comparisons for immediate effects (cT1 to cT2), longer term effect (cT1 to cT3) and sustained effects (cT2 to cT3). Sidak Type-I error rate adjustment (which has higher power than Bonferroni) will be applied for the multiple pairwise time point comparisons.¹²² Additionally, longer term sustained effects will be captured for the immediate Tele-Savvy group using the additional follow-up times at T4 and T5 for this group. The proposed study design has the advantage of capturing 3 "baseline" time points for the wait-list attention control and usual care groups which will provide an excellent opportunity to evaluate what if any potential "placebo" effects there may be from being enrolled in this type of study.¹²³ These initial

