data captured at T1-T2-T3 for the delay group will also be used to evaluate any potential decline occurring during this time period. All model assumptions will be tested; grand mean centering used to help combat multicollinearity between variables; and standard diagnostic tests and influence statistics used to test the distributions of the residuals. MLM models utilize all available data for all participants at each time point and have the advantage of adjusting for the missing data over time, where repeated measures ANOVAs do not. Further covariate predictors of missingness over time will be included to additionally adjust for these confounders¹²⁴ To aid in final interpretation we will include the 95% confidence intervals around means by intervention group and time period. SPSS v.22 will be used for all analyses at the 5% significance level.¹²²

Aim 3(b). To test the mediating effect of mastery on Aim 1 & 2 outcomes, we will employ the PROCESS add-on module for SPSS¹²⁵ which includes performing the combined approaches of Baron and Kenney, the Sobel test, as well as semi-parametric estimation and testing of the Sobel test through bootstrapping. The focus will be on both the immediate (T2 for immediate Tele-Savvy group and T4 for attention control and usual care groups pooled together) and sustained (T3 for immediate Tele-Savvy group and T5 for attention control and usual care groups pooled together) effects of Tele-Savvy on the mediating measure of mastery on the Aim 1 and Aim 2 outcomes of caregiver burden, depression, anxiety, and dyadic relationship and PLWD BPSD, agitation, mood, and quality of life. These indirect/mediation effects will also be tested and evaluated using structural equation modeling via AMOS v.22.¹²⁶

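### Covariates for the Aim 1–3(a) models are chosen by significance tests on the trial's own data, with neither the set nor its by-visit form fixed in advance

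*Combined protocol and SAP*

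**What the plan says.** The Analytic approach paragraph of the Data Management and Analysis Plan has two screening steps. Completers are compared with non-completers, and the arms with each other, the latter "by study arm (immediate/attention control/usual care) as a randomization check". Predisposing factors are then tested against baseline data and against change in outcomes. The rule that follows is: "Where significant baseline associations are detected, these potential confounders will be controlled in subsequent tests of major hypotheses through use of covariates/model adjustments". It does not say which association counts, at what threshold, or in what form the covariate enters.

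The paragraph on Aims 1, 2 and 3(a) adds two rules. In the additional pooled analysis, which aligns all arms on the start of Tele-Savvy, adjustment is again triggered by a test: "If there are significant differences between or among the 3 groups at the time point immediately prior to receipt of the intervention (cT1" in the plan's notation). Later, on missing data: "Further covariate predictors of missingness over time will be included to additionally adjust for these confounders". Those predictors are not named and not restricted to baseline.

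The primary test is identified in the Power Analysis section: "for the primary intervention test (group-by-time effect) comparing the outcomes of the three group changes from T1 to T2 to T3". The model is a mixed model with a participant random effect and cohort as a fixed effect. No baseline covariate is named for it.

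**The concern.** Three consequences follow.

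- **A model settled after the data are seen.** Covariates that depend on test results leave the final model open until then, and the model can differ between burden, depression, anxiety, care-recipient outcomes and mastery. Under randomisation, a baseline arm difference arises by chance. Adjusting only for covariates that happen to differ ignores those that predict the outcome.
- **Adjustment that may not reach the primary contrast.** A covariate that is constant over time and entered only as a main effect cancels out of within-person change, and the primary test concerns change.
- **An open door for post-randomisation variables.** The plan records videoconference attendance and video viewing. Usual care has no program before month 6, so these variables are tied to arm over T1–T3. If one entered as a missingness predictor, it would absorb part of the program effect.

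At stake are a few points of power, a model fixed in advance, and protection of the arm comparison against an avoidable bias.

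**Working it through.** **1. The plan's own figures.** Inputs from the Power Analysis section: "final expected sample size of 215 (86, 86, 54 in Tele-Savvy (TS" and the other arms), and "at 80% power and 5% significance level, small-to-moderate effect sizes, Cohen's $f = 0.21-0.24$ may be detected". Using noncentral F with λ = N·f² and N = 215, the λ needed for 80% power gives:

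- group (2, 212 df): √(9.772/215) = 0.213
- time (2, 424 df): √(9.703/215) = 0.212
- group-by-time (4, 424 df): √(12.069/215) = 0.237

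The stated range is reproduced. No covariate enters it, so nothing below changes the sample size. (The listed arms sum to 226, not 215; this point does not depend on that.)

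**2. Chance flags.** With k independent arm comparisons at 5% (k is assumed; the plan gives no count), the chance of at least one false flag is 1 − 0.95^k: 23% for 5, 40% for 10, 64% for 20.

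**3. Power for change.** Assumptions: Tele-Savvy v attention control, 86 per arm, effect 0.4 SD of change, six covariates jointly explaining R² = 5% or 15% of the variance in change.

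- Unadjusted: expected statistic 0.4·√(86/2) = 2.623; power 74% (170 df).
- All six always included: 2.623/√[(1 − R²)(1 + 6/163)], where 163 = 172 − 2 − 6 − 1 allows for estimating six slopes. R² = 5%: 2.643, power 75%. R² = 15%: 2.794, power 79% (164 df).
- Imbalance trigger: on average 6 × 0.05 = 0.3 covariates enter, so the model is close to the unadjusted one.

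Simulated power, R² = 5% / 15%:

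| Rule | Simulation | Repeat, 10,000 trials |
|---|---|---|
| Adjust if arms differ | 73% / 72% | 73.7% / 74.6% |
| Adjust if associated with outcome change | 75% / 77% | 74.2% / 77.2% |
| Fixed set | 75% / 77% | 74.5% / 79.5% |

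A fixed set gains about 1–2 points at R² = 5% and about 5 at 15% over the imbalance trigger, and 0 to about 2 over the association trigger. Null rejection is about 5% for every rule.

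**4. Main effects and group-by-time.** If Y(i,t) = … + γX(i) + …, then Y(i,3) − Y(i,1) contains no γX(i). A simulated random-intercept model (108/108/54, three visits, 500 trials per setting, within-person correlation from "given moderate correlation between measurement pairs of $r=0.3-0.5") confirms this:

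- Complete data: the largest difference in the group-by-time F is about 3e-7, which is numerical error.
- 20–25% dropout related to the covariate: the T3 contrast moves on average 0.08–0.11 SE, at most 0.50 SE. The 5% decision changes in 0.8–1.6% of null trials and 2.2–5.8% of trials with a 0.4 effect.
- Assumed 0.3 SD arm imbalance in a covariate that predicts change (slope 0.5), no true effect: rejection is 10.4% unadjusted, 10.4% with main effects and 4.2% with covariate-by-visit terms. With 20% dropout it is 13.0%, 13.0% and 6.8%.

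The last result is conditional on that imbalance. It is not the type I error over all randomisations.

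**5. A post-randomisation covariate.** Let arm shift the covariate by a and the covariate shift the outcome by b, with a total effect of 0.40. Conditioning leaves 0.40 − a·b:

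| a | b | 0.40 − a·b | Simulated with it | Simulated without it |
|---|---|---|---|---|
| 0.3 | 0.4 | 0.28 | 0.28 | 0.40 |
| 0.5 | 0.4 | 0.20 | 0.19 | 0.39 |
| 0.5 | 0.6 | 0.10 | 0.09 | 0.40 |
| 0 | 0.4 | 0.40 | 0.40 | 0.39 |

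The values of a and b are assumptions. The bias exists only if arm affects the covariate.

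**The case against.** The strongest reply is that the adjustment sentence directly follows the screen of predisposing factors against baseline data and change, so its nearest meaning is association with outcome, not arm imbalance. On that reading strong prognostic covariates are nearly always selected and little is lost. This stands as a reading, but the arm tests sit one sentence earlier and the wording does not decide between the two. On either reading the data choose the model.

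Four stronger conclusions are tempting, and the documents do not support them.

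- **Adjustment cannot affect the primary test.** The plan does not say main effects only; its wording allows other model adjustments. Exact cancellation also needs complete data, whereas the plan expects 20% attrition (Power Analysis) or 25% (Limitations and Challenges) and uses all available data.
- **Power losses near 10 points.** A single-endpoint comparison under an imbalance trigger, with covariate-outcome correlation 0.5, gives 75% against 85% when always adjusted. That is not the group-by-time test. With an outcome-association trigger the same setting gives 85%.
- **The plan will adjust for attendance or viewing.** It never says so. It presents them as adherence and dose monitoring, and the only completer comparison it describes is of baseline differences. The missingness rule is a gap in wording.
- **All three rules are significance tests bearing on the primary analysis.** The missingness rule states no significance criterion. The cT1 rule governs only the pooled analysis. There, cT1 is T3 for both wait-list arms, so differences at that point need not be chance.

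The false-flag percentages also depend on an assumed number of independent tests.

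**Conclusion.** The concern holds in a limited form. The Aim 1–3(a) covariates are selected from the trial's own data, with no named set, threshold or form, and the pooled analysis has a second significance trigger. The power cost is roughly 0 to 5 points: least if outcome association is the trigger, most if arm imbalance is the trigger and the covariates explain about 15% of the variance in change. This rests on an assumed 0.4 SD effect, six covariates and R² of 5–15%. A reader might infer inflated type I error; none is shown on either reading.

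The form of adjustment matters as much as the set. Main effects alone would have little or no influence on group-by-time, so the by-visit form has to be written down. The missingness rule would bias the arm effect toward zero only if a post-randomisation variable affected by arm were entered. The text permits this but does not state it.

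**What to change.** - Replace the significance trigger in the Analytic approach paragraph with one short, named set of baseline covariates already collected. IQCODE, the Lawton ADL/IADL score and co-residence are candidates; the final list is the study team's choice.
- Enter each with its visit interaction in every Aim 1–3(a) model, whatever its p-value.
- Describe baseline characteristics by arm, but drop arm significance tests as a basis for adjustment.
- In the pooled analysis, state in advance whether and how cT1 differences are adjusted for, without a test deciding it.
- Limit missingness predictors in the outcome model to named baseline variables. Use post-baseline ones only as auxiliaries in a multiple-imputation sensitivity analysis.

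**Cost.** SAP wording, with no change to sample size or data collection. Over three visits a single-parameter covariate takes one main effect and two interaction terms, so six take 6 × 3 = 18 parameters per model, and more if any has several categories. That is small against about 215 × 3 = 645 observations, but it is a reason to keep the set short.

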Tele-Savvy. Tele-Savvy engages groups of (on average) six dementia family caregivers in a program that extends over 43 days (see figure below). The program begins with a scheduled 75-minute group videoconference led by one or two facilitators; similar group videoconferences then take place each of the next six weeks (i.e., seven video-conferences). In between the video-conferences, caregivers receive daily emails with links to 5-20 minute on-line video lessons that they can watch on their own schedule and as often as they wish (there are 36 unique video lessons; the Tele-Savvy story board (Appendix A) delineates the content of these video lessons). The curriculum includes all of the elements of SCP plus material from an advanced program (SCP-II)⁹⁶ and from Co-PI [name]' caregiver self-care projects (see below). The videoconferences incorporate the coaching/debriefing feature of SCP to allow caregivers to report enactment of learned and self-developed management strategy behaviors into their own caregiving. The videoconferences include talks and exercises and also allow caregivers to raise questions. Each daily video presents a teaching point linked to the overall curriculum. All follow the same format: experts provide instruction about a topic, and the lesson is carried forward by brief, scripted talks by other experts or is enacted in brief vignettes in which a fictional family caring for a father living with Alzheimer's demonstrates – at various stages of the illness – effective caregiving techniques linked to the day's teaching points.

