Monthly team videoconferences will be conducted to discuss project progress, recruitment, data collection and analysis, and other issues. The Emory coordinating team will meet weekly. The site co-

investigators and [name] will also meet annually at the ADC Directors' meeting. Additional Data Safety Monitoring Board committee meetings will be held mid-year in years 2 and 3.

Scientific Approach

Design. We aim to enroll 375 subjects in 25 cohorts of 15 subjects each, starting in project month 9 (see project timeline). We expect to enroll, on average, four cohorts per quarter through project year 2 1/2. Recruitment of every 2 cohorts (30 participants total) is scheduled to take place every 6 weeks. We will use a three-arm design with participants randomly assigned on a 2:2:1 ratio to immediate participation in the Tele-Savvy intervention (N=108), immediate participation in an attention control condition (Healthy Living) (N=108), and a usual care condition (N=54). There will be five data-collection points evenly spaced across 12 months. Those in each cohort's intervention condition will take part in Tele-Savvy immediately following baseline data collection. Those in the attention control and usual care conditions will take part in Tele-Savvy after a delay of 6 months (following the 6-month data collection point). Below, we describe the preparation activities in which we will engage (facilitator training and material revisions) and then describe the trial itself. Four NIA-supported Alzheimer's Disease (Research) Centers will collaborate in recruitment, and Emory University will serve as the coordinating center. Emory will be responsible for randomization of subjects (recruits from all sites will be pooled together for randomization), for delivery and fidelity monitoring of the intervention and attention control condition, and for all data gathering and analysis.

Please see the added document for Amendment 8.

Project Timeline, by Quarters

Main Project Activities	Year 1				Year 2				Year 3				Year 4			
	1	2	3	4	1	2	3	4	1	2	3	4	1	2	3	4
Staffing; Training; Finalizing																
DSMB scheduled meetings		X			X				X				X			X
Enroll 18 cohorts (15 each) + Acquisition	30	60	90	120	150	180	210	240	270							
Data Collection																
Data Cleaning and Analysis																
Dissemination																

Preparation.

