non-verbal cues and has to employ a more directive style to manage group dynamics, such as “calling on” individuals to report on their home activities or to determine if they have questions. One or more facilitators will be trained to conduct the videoconference component of the “Healthy Living” attention control condition. Drs. [name] and [name] will develop and conduct the training program for the attention control facilitator(s). As part of training, each facilitator will lead, as appropriate, a dry run of Tele-Savvy and the Healthy Living programs. The lead investigators will observe these dry runs, providing coaching and additional training, as needed. Former participants of the in-person Savvy Caregiver program will be invited to participate.

Facilitators will be assigned to lead cohort-based Tele-Savvy groups based on their time availability; the leader will be consistent across the seven sessions of the cohort’s participation. No facilitator will ever lead more than two groups at a time. Over the course of the project, the investigators and the Project Coordinator will monitor Tele-Savvy and Healthy Living fidelity by observing and evaluating ≥ 3 individual group sessions per facilitator per cohort using a fidelity checklist. Fidelity will be evidenced by $\geq 80\%$ adherence to a group session compliance checklist. (Appendix D) Compliance ratings $< 80\%$ and median caregiver ratings for session quality of < 8 will signal [name] and [name] to discuss with facilitators, conduct PRN remedial training and observe/participate in the next two sessions or until ratings adherence is achieved and maintained.

Facilitators will be hired part-time or as consultants as a way to demonstrate that fidelity to the Tele-Savvy Program curriculum can be maintained across interventionists. Additionally, working with part-time facilitators in this study will provide evidence on the feasibility of similar employment of facilitators in other settings, such that Tele-Savvy may be administered by employees of existing organizations (e.g., social workers) as a part of their preexistent job description rather than their sole responsibility. Such incorporation of Tele-Savvy administration into the whole job description is more likely to make Tele-Savvy adoptable in a variety of settings rather than reliance on full-time facilitators.

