Wait List Attention Control Group Condition and Participation. The attention control condition consists of video and text materials on exercise, diet, and healthy living drawn from the NIA Go4Life program. While these materials provide important and beneficial information, we believe they will not affect our postulated key mediators (mood, mastery and care recipient quality of life). They will provide equal attention, but should not confound the trial. The same number of brief modules as employed in Tele-Savvy (36) will be provided over the course of six weeks; videos will emerge on Canvas site weekly in a manner similar to the Tele-Savvy condition described above. Likewise, navigator will send attention control participants weekly reminder e-mails to log into Canvas and view daily videos. All attention-control participants will convene weekly for a videoconference that will mirror Tele-Savvy videoconference in format and length but will differ in content. Specifically, attention control videoconferences will not contain any information on caregiving strategies, but rather will center on the application of healthy living strategies. A standard structure of each videoconference will be employed by attention-control facilitators: (1) Facilitators greet and check in with each of the caregivers; (2) coaching and debriefing (e.g., hearing how (after the first week) caregivers did with the homework, answering questions and/or responding to feedback about the week's material; (3) review of key points and concepts from the week's video sessions and introduction of new material; (4) reports on any activities that caregivers may have implemented based on the Go4Life materials; (5) provision of homework assignments and adjournment.

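### Tele-Savvy and the attention control are delivered in live groups, but neither the analysis model nor the power calculation allows for correlation within delivery groups

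*Combined protocol and SAP*

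**What the plan says.** The section on Aims 1, 2 and 3(a) gives the model: "We will employ multi-level mixed effects models (MLM) with random (participant) and fixed (cohort) effects". The three arms are compared over T1 to T3. A second analysis pools all arms around their own receipt of Tele-Savvy (cT1 to cT3). No term is named for the videoconference group or the facilitator.

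Delivery is as follows:

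- **Tele-Savvy.** "Tele-Savvy engages groups of (on average) six dementia family caregivers" (Tele-Savvy section). Under Facilitator Training, "the leader will be consistent across the seven sessions", and "No facilitator will ever lead more than two groups at a time".
- **Attention control.** "All attention-control participants will convene weekly for a videoconference" of the same format and length (Wait List Attention Control section). Group size is not stated. It would be about six if 2:2:1 holds within cohorts of 15.
- **Usual care.** Individual calls until month 6 (Subject Randomization section), then the same group Tele-Savvy programme (Usual Care section).

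The power section says that Cohen's f of 0.21–0.24 "may be detected for the main effects for group, time and group-by-time interaction effects", using a correlation of 0.3–0.5 between repeated measures. It gives a detectable d of 0.19 from "a total estimated 215 subjects to perform a pre-post test". It contains no ICC and no design effect. It is based on 270 enrolled, whereas the Design section says "We aim to enroll 375 subjects in 25 cohorts of 15 subjects each".

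**The concern.** Caregivers who meet weekly in the same small group share a leader, peers and discussion. The programme's theory counts on this: the Savvy Caregiver description lists learning from seeing a peer succeed, and facilitators are trained to build connection within the group. Outcomes in one group may therefore be correlated after the programme starts.

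Over T1 to T3 this is a partially nested design, with two arms grouped and one not. Each cohort contains all three arms, so a cohort effect removes only what the arms share. It leaves the effect of one particular Tele-Savvy or attention-control group in the arm contrast, and nothing in the standard error accounts for it. If cohort enters only as an intercept, which is an assumption because the plan does not say, it drops out of the group-by-time test altogether.

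Two things are at stake. P-values and 95% intervals would be too optimistic, most of all for Tele-Savvy versus attention control, the comparison that separates caregiving content from attention. The power stated for 215 analysed would also be too high. The pooled analysis is exposed as well, because everyone in it receives Tele-Savvy in a group.

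**Working it through.** **Inputs from the documents.** Groups of about six; 2:2:1 allocation in cohorts of 15, so 6/6/3; 270 enrolled; 20% attrition; 86 retained in each of the two larger arms; 5% significance (taken as two-sided) and 80% power; correlation between visits 0.3–0.5.

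**Assumed.** ICC of 0.02, 0.05 or 0.10, and retained group size m = 6 × 0.80 = 4.8.

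**1. The plan's own figures.**

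- 270 × 0.80 = 216, against 215 stated.
- Pre-post: d = (1.960 + 0.842)/√215 = 2.802/14.66 = 0.191, against 0.19 stated.
- Noncentral F with λ = N·f² and N = 215 gives 80% power at f = 0.213 (group), 0.212 (time) and 0.237 (interaction), against 0.21–0.24 stated.

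The figures reproduce when caregivers are treated as independent, that is, at ICC 0.

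**2. Design effect.** DE = 1 + (m − 1) × ICC. Effective n per arm = 86/DE. Type I error for Tele-Savvy versus attention control = 2 × [1 − Φ(1.96/√DE)]. Pooled detectable d = 0.191 × √DE, assuming delayed groups of the same size and the ICC applied to change scores.

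| ICC | DE | Effective n per 86 | Type I error | Pooled d |
|---|---|---|---|---|
| 0 | 1.00 | 86 | 5.0% | 0.19 |
| 0.02 | 1 + 3.8 × 0.02 = 1.08 | 80 | 5.9% | 0.20 |
| 0.05 | 1 + 3.8 × 0.05 = 1.19 | 72 | 7.2% | 0.21 |
| 0.10 | 1 + 3.8 × 0.10 = 1.38 | 62 | 9.5% | 0.22 |

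With unattrited groups of six, DE is 1.10/1.25/1.50 and type I error 6.2/8.0/11.0%. The Subject Randomization section speaks of equal numbers per arm. Read that way (5/5/5, 4.0 retained), DE is 1.06/1.15/1.30.

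**3. Simulated type I error.** T1 to T3, 6/6/3 per cohort, 20% attrition, r = 0.3 and 0.5, and a group effect after baseline in Tele-Savvy and attention control only. The planned participant-level model was tested on within-person contrasts, from which a cohort intercept cancels. Ranges are over r.

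| Test | ICC 0 | 0.02 | 0.05 | 0.10 |
|---|---|---|---|---|
| Tele-Savvy vs attention control, T1-to-T3 change, 18 cohorts | 4.2–5.4% (18 or 25 cohorts) | 5.4–5.9% | 7.0–7.8% | 8.3–10.6% |
| Same, 25 cohorts | as above | 5.3–5.8% | 7.3–7.8% | 9.3–10.6% |
| Three-arm group-by-time F test | 5.0–5.4% | 5.4–5.6% | 6.3–6.8% | 7.5–9.0% |
| Tele-Savvy vs usual care | – | 5–6% | 6–6.5% | 6.5–8% |

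The first two rows used 10,000 runs and the F test 20,000.

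**4. Cohort crossed with time.** A separate simulation (r = 0.4, 3,000 runs per cell, Monte Carlo error about 0.4 points at 5%) gave cohort its own time effects. At ICC 0.02/0.05/0.10, Tele-Savvy versus attention control (baseline against the mean of T2 and T3) rejected in 6.2/7.3/11.2% of runs, and the F test in 4.8/6.3/7.8%. Crossing cohort with time does not remove the inflation.

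**5. Power of the three-arm test.** Size-adjusted, with the effect set to give about 80% at 18 cohorts and ICC 0:

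| Basis | ICC 0.02 | 0.05 | 0.10 |
|---|---|---|---|
| 270 enrolled (about 216 analysed) | 77.0–77.8% | 73.8–75.2% | 67.3–71.3% |
| 375 enrolled (about 300 analysed) | 90.7–91.0% | 88.3–88.4% | 82.4–85.7% |

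**The case against.** The strongest reply is that the size depends on an ICC that the documents do not supply, and that it may be small. Lessons are watched alone, sessions follow a fixed agenda, and fidelity is monitored. At ICC 0.02 the three-arm test is at 5.4–5.6%, hardly distinguishable from nominal, and at ICC 0 the plan is valid. This stands, and it is why the concern is conditional. It does not justify assuming zero, which the documents neither state nor support.

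Second, if 375 are enrolled, the three-arm test keeps 80% power over the whole assumed range. That also stands, so the power complaint applies to the 270 basis that the power section uses. However, the larger number is not presented as a clustering allowance, and more cohorts do not reduce type I error.

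Third, the formula applies the ICC directly to change scores. With a group effect only after baseline and r = 0.3, the variance of change is 2 × (1 − 0.3) = 1.4. The relevant ICC is then ICC/1.4, which gives DE 1.05/1.14/1.27 and type I error of about 5.6/6.6/8.2%. At r = 0.5 that variance is 1 and the table in step 2 is unchanged. This narrows the estimate without removing it.

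Fourth, the plan does not say that cohort is only an intercept. Step 4 shows that crossing it with time does not rescue the test. A fixed effect for every cohort-by-arm group would not help either, because the arm effect could then not be separated from its groups.

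Finally, the Design section refers to a document for Amendment 8 that is not part of the text reviewed. The conclusion is limited to the supplied text.

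**Conclusion.** The concern holds. The specified model omits a source of correlation that the delivery format makes plausible, and the stated power assumes it away. For Tele-Savvy versus attention control, true type I error at a nominal 5% would be about 5–6% at ICC 0.02, 7–8% at 0.05 and 8–11% at 0.10. The effect is smaller for the three-arm test and for Tele-Savvy versus usual care. On the 270 basis, three-arm power falls from 80% by about 2–3, 5–6 and 9–13 points. On the 375 basis it stays above 80%. The pooled detectable d moves from 0.19 to 0.20–0.22.

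These sizes rest on the assumed ICCs, 4.8 retained per group, and attention-control groups of the same size as Tele-Savvy groups. The problem is slight at 0.02 and material from about 0.05. It should be fixed, ideally before outcomes are compared by arm, so that the choice of model cannot depend on the results.

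**What to change.** **Analysis (Aims 1, 2 and 3(a)).**

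- Add a random effect for the actual delivery group, on post-baseline visits in the group-delivered arms. Use a recorded group identifier and do not infer it from cohort and arm, because caregivers needing Saturday or evening sessions are randomised in a separate block.
- For T1 to T3, treat each usual-care caregiver as a singleton (partially nested model). Use Satterthwaite or Kenward-Roger degrees of freedom.
- Apply the same term to the delayed Tele-Savvy groups in the pooled cT1–cT3 analysis and at T4 and T5. Former attention-control caregivers join a second group after month 6, and their T3 value may carry the first group's effect, so keep both identifiers for them.
- Add a sensitivity analysis for facilitator, since one person may lead two groups at once.

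**Power section.** First settle whether 270 or 375 is the basis, and whether allocation is 2:2:1 or equal. These are separate inconsistencies, but both feed the calculation. Then restate power or detectable effects with 1 + (m − 1) × ICC, where m is the retained group size, over a declared ICC range.

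**Cost.** The group identifier can be taken from the attendance records the navigator already keeps, and a mixed model is already planned. The main comparison needs one extra random term; the pooled analysis needs somewhat more specification. Intervals will be slightly wider, the power statement less favourable, and the variance component may be estimated at zero.
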